**Figure 1: Digital consent pack survey branching logic**

*Additional consent for face-to-face meetings:* As part of the face-to-face visits additional consent will be sought from an additional biological parent (if available; Parent Consent for child), an unaffected sibling (Sibling Consent Form) and the child’s teacher (Teacher Consent Form). Additional consent is optional, families will still be able to take part in the face-to-face visits if additional family members and the teacher consent is not obtained.

### **Withdrawals**

Should participants not wish to take part in the follow up study, they will be offered the opportunity to withdraw. However, data collected up until withdrawal (i.e., that gathered in the course of IMAGINE-1) will remain in the study.

### **5.3 Screening and Eligibility Assessment**

Screening and eligibility assessment was carried out during the recruitment phase in IMAGINE-1. All participants recruited in IMAGINE-1 are eligible to take part in IMAGINE-2.

Screening and eligibility of families self-referring to IMAGINE-2 will be established based on the criteria described in section 8.1 by a trained study researcher.

## 5.4 Baseline Assessments

Baseline assessments conducted during **IMAGINE-1** (2014-2019) included:

### **Workstream 1 (full cohort online):**

**Completed by:** Parents/caregivers of children with a rare genetic disorder and associated intellectual disability.

**Completion time:** ~3h parents. Questionnaire answers are automatically saved and participants were advised that they did not need to complete the assessments in one sitting. In IMAGINE-1 participants typically completed the baseline questionnaires at their convenience, in smaller chunks of time.

**Location:** Families can complete the questionnaires online at home. Should families not have access to the internet, the questionnaires will be sent in paper form by post or administered over the phone.

### **Assessments:**

- **Development and Wellbeing Assessment** (DAWBA; 2-2.5h)

The DAWBA will be used to collect information on the child's behavioural adjustment and mental health. The DAWBA has been used both in UK national and international surveys (Ford et al., 2003; Green et al., 2004; Heiervang et al., 2008; Emerson et al., 2007).

This methodology has been used successfully to gather data of high quality by parental on-line report. We will use a validated automated diagnostic algorithm system devised for this purpose, compatible with ICD-10/DSM-V. The DAWBA is available in 26 languages (<http://www.dawba.com/>) and we do not intend to exclude families on the basis of ethnicity or inability to speak/understand English.

- **Strengths and Difficulties Questionnaire** (SDQ; 5 min)

The SDQ is a brief behavioural screening questionnaire about 4-18 year olds (Goodman et al., 2011). Many child and adolescent mental health clinics now use the SDQ as part of the initial assessment.

- **Adaptive Behavior Assessment System, Second Edition** (ABAS-3; 30 min)

The ABAS-3 is a measure of adaptive function (Harrison and Oakland, 2003). It covers three broad domains (conceptual, social and practical). Within these domains, it assesses 10 skill areas. Items focus on practical, everyday activities required to function, meet environmental demands, provide self-care, and the ability to interact with others effectively and independently. It is appropriate for use up to 89 years of age.

- **Health Questionnaire** (30 min)

Physical development, medical comorbidity and service usage will be recording using an online questionnaire developed by IMAGINE ID. Data include: birth, physical development and anomalies, metabolic systems, sensory abnormalities, psychomotor development, communication skills, services and intervention, medical history. Free text entry is available. Ethnicity and immigration status will also be recorded (the latter a recently identified risk factor for child mental health).

- **Draw-a-Person: Quantitative Scoring System** (DAP:QSS, 10 min)

The draw a person test is a non-verbal test to evaluate intelligence in children. Participating children were asked to complete 3 drawings: a picture of a man, a woman and themselves. The instructions are minimal and easy to understand: "I want you to make a picture of a person. Make the very best picture that you can. Take your time and work very carefully. Try very hard and see what a good picture you can make." For each picture the child is asked to draw a full person (e.g. head to feet). There is no time limit, but children rarely take longer than 10-15 minutes to complete all 3 drawings. The DAP:QSS is both valid and reliable (Goodenough, 1963; Naglieri, 1988; Naglieri and Maxwell,

1981; Jolley, 2010) and correlates with face to face IQ measures including the WISC-R and WISC-III (Abell, Wood, & Liebman, 2001).

***Workstream 2 (subset of cohort with additional face to face assessments):***

Baseline assessments conducted during **IMAGINE-1** (2014-2019) included:

Questionnaire-assessed child psychopathology, prenatal factors and pubertal development, self-report psychopathology

The main-caregiver will provide information on the child and their environment, including:

1. Family size and structure, social class, pregnancy and child birth (age at birth, birth weight, ante- and perinatal health problems, smoking and alcohol use, as collected by with the modified Lewis scale) (Lewis et al., 1987).
2. Life Events Checklist to screen for possible traumatic events experienced by the child (Johnson et al., 1980).
3. Family relationship quality i.e. overall family relationship quality (Family Environment Scale; Moos et al., 2013) and parent child relationship quality (warmth and hostility)(Iowa Family Interaction Rating Scales; Melby et al., 1997).
4. Child prosocial and antisocial behaviour, ADHD and emotional symptoms by completing the Strengths and Difficulties Questionnaire (SDQ; Goodman et al., 2011).
5. Child development and behavioural problems with the Developmental Behaviour Checklist (DBC) which was developed specifically for children with intellectual disability.
6. The Social Communication Questionnaire (SCQ; formerly Autism Screening Questionnaire (ASQ)) will be used to screen for autism.
7. Child pubertal development will be obtained by Peterson assessment.
8. Development Coordination Disorder using the Development Coordination Disorder Questionnaire (Einfeld et al., 2002) and the Children's Physical Activity Questionnaire (cPAQ) (Corder, 2009).
9. Child eating style and behaviour, with the Child Eating Behaviour Questionnaire (CEBQ; Carnell et al., 2007) and the Hyperphagia Questionnaire (HQ) (Fehnel, 2015).
10. Epilepsy and seizures using the Epilepsy screening questionnaire (Ottman et al., 2010).
11. Record of medication, operations, contact details of GP, school and screening questions about current state of health.

Interview-assessed child psychopathology:

- Child and Adolescent Psychiatric Assessment (P-CAPA; Angold et al., 1995): will be conducted with the main-caregiver. The CAPA (duration 2-3 hours) provides DSM-IV and ICD-10 diagnoses of all behavioural and psychiatric problems (including detailed assessment of psychotic symptoms), except autism. A child self-report version of the CAPA (C-CAPA) will be used with the children to ascertain psychotic symptoms, mood and anxiety symptoms
- Structured interview for Prodromal Symptoms (SIPS; Miller et al., 2002): conducted with older children to obtain information on prodromal psychosis symptoms
- Autism Diagnostic Interview–Revised (ADI-R; Rutter et al., 2003): will be conducted where screening by SCQ is positive (duration 1-2 hours). If probands screen positive for autism, in combination with the ADI-R interview conducted with the parents, we will offer the parent the possibility to conduct an observational assessment of the child, to establish autism, using the Autism Diagnostic Observation Schedule (ADOS; Lord et al., 1989). The ADOS is a semi-structured, standardised assessment of communication, social interaction and play. It provides a series of standardised contexts in which the child's social, communication and repetitive, stereotyped behaviours can be observed. Standardised toys and activities are used to present opportunities for social and communicative interaction with the examiner.

Interview-assessed own and partner psychopathology:

- The 'Family Structure and function' section of the CAPA will be conducted with the primary caretaker regarding any psychiatric problems faced by themselves and the second caretaker, if applicable. This section provides DSM-IV and ICD-10 diagnoses of the following psychopathology: depression, anxiety, panic disorders, eating disorders, drug or alcohol use and psychosis.

Teacher reports:

- Teachers will be asked to complete a consent form agreeing to complete a questionnaire about their pupils if the participant agrees that the teacher can be approached. We provide a consent form for teachers. Once agreed teachers are asked to complete a brief teacher version of the Strengths and Difficulties questionnaire (SDQ) and further information on child development specifically suited for cognitively impaired children with the Developmental Behaviour Checklist (DBC).

Neurocognitive assessment of children:

- Wechsler Abbreviated Scale of Intelligence (WASI; Wechsler et al., 1981): to assess children's IQ
- Wisconsin Card Sorting Test (WCST; Heaton et al., 1981): to assess executive function
- Cambridge Neuropsychological Test Automated Battery (CANTAB)

**5.5 Subsequent Visits****Workstream 1 (full cohort - online):**

**Completed by:** Caregivers/parents will be asked to complete short questionnaires on an annual basis and more in-depth questionnaires at a 5 year follow up (Figure 2).

**Completion time:** Short annual follow up ~25mins; once only 5-year follow-up assessment ~3h. Questionnaire answers will be automatically saved. Participants will be encouraged to complete the questionnaires at their pace and convenience. They will be able to complete the questionnaires in multiple sittings.

**Location:** Families can complete the questionnaires online at home. Should families not have access to the internet, the questionnaires will be sent in paper form by post or administered over the phone. Previous experience indicates this provision applies to less than 1 in 10 participants.

**Online tools:** Questionnaires will be sent to the participant via a RedCap link sent by the researcher team. The link takes them to the questionnaires. These can be 'saved' and do not need to be completed in one go. Participants can contact the researchers and full support will be offered to participants encountering any issues whilst completing the questionnaires.

IMAGINE-2					
Year recruited	2020	2021	2022	2023	2024
Follow up	Wave 1	Wave 2	Wave 3	Wave 4	Wave 5
2014/2015 N= 552	DAWBA + ABAS-3	Annual Follow- up	Annual Follow- up	Annual Follow- up	Annual Follow- up
2016 N= 621	Annual Follow- up	DAWBA + ABAS-3	Annual Follow- up	Annual Follow- up	Annual Follow- up

2017 N= 803	Annual Follow-up	Annual Follow-up	DAWBA + ABAS-3	Annual Follow-up	Annual Follow-up
2018 N= 900	Annual Follow-up	Annual Follow-up	Annual Follow-up	DAWBA + ABAS-3	Annual Follow-up
2019 N= 526	Annual Follow-up	Annual Follow-up	Annual Follow-up	Annual Follow-up	DAWBA + ABAS-3

Figure 2: Assessment schedule based on year of recruitment

### **Annual follow-up assessments:**

All consenting participants will be followed up annually to complete an online survey. The survey will be comprised of four short questionnaires. The survey will be administered using the RedCap online data collection tool which is hosted on the UCL Data Safe Haven. The annual assessments combined will take no longer than 30 minutes to complete. The assessments have been shown to be acceptable to families as part of IMAGINE-1:

#### **1. Strengths and Difficulties Questionnaire (SDQ, 5 min)**

The SDQ will allow us to understand the trajectory of behavioural adjustment of their child over a 5 year period. The SDQ is a brief behavioural screening questionnaire about 4-18 year olds (Goodman et al., 2011). Many child and adolescent mental health clinics now use the SDQ as part of the initial assessment.

#### **2. Everyday Feelings Questionnaire (EFQ, 5 min)**

The EFQ is a short 10-item measure of psychological wellbeing and distress in adults. It is widely used and well-validated (Uher and Goodman, 2009; Goodman and Goodman, 2009).

#### **3. Family Life Questionnaire**

The Family Life Questionnaire (FLQ) is a brief 14-item measure of family functioning. It differs from other family function assessments by measuring the experience of family in relation to a single child (Last, Miles, Wills, Brownhill, & Ford, 2012).

#### **4. Wessex scales (5 min)**

The Wessex Scales will allow us to measure adaptive function and severity of the intellectual disability (Kushlick, Blunden & Cox, 1973). The measure assesses self-help skills, literacy, mobility and incontinence. The different domains can be summed to derive a 'Social and Physical Incapacity' score and 'Speech, Self-Help and Literacy' score. It is widely used in studies of intellectual disability.

#### **5. Demographic updates (10 min)**

This questionnaire will allow us to understand changes in circumstances over the 5 year period. The questionnaire will include questions on changes in the child's address, mental health diagnoses, schooling and support received (Appendix B).

### **Feedback to families:**

In IMAGINE-1 parents were sent a report summarising their child's strengths and difficulties. After every annual follow up during IMAGINE-2 parents will receive a report summarising their child's current strengths and difficulties (Appendix C). Participants will be emailed a copy of their report within a month of having completed the questionnaire.

### **5 year follow up assessment:**

Participants will also be asked to complete the DAWBA and the ABAS, 5 years after baseline completion.

- **Development and Wellbeing Assessment (DAWBA; 2-2.5h parent-report)**

The DAWBA will be used to collect information on the child's behavioural adjustment and mental health. The DAWBA has been used both in UK national and international surveys (Ford et al., 2003; Green et al., 2004; Heiervang et al., 2008; Emerson et al., 2007).

This methodology has been used successfully to gather data of high quality by parental on-line report. We will use a validated automated diagnostic algorithm system devised for this purpose, compatible with ICD-10/DSM-V. The DAWBA is available in 26 languages (<http://www.dawba.com/>) and we do not intend to exclude families on the basis of ethnicity or inability to speak/understand English.

- **Adaptive Behavior Assessment System, Second Edition (ABAS-3; 30 min)**

The ABAS-3 is a measure of adaptive function (Harrison and Oakland, 2003). It covers three broad domains (conceptual, social and practical). Within these domains, it assesses 10 skill areas. Items focus on practical, everyday activities required to function, meet environmental demands, provide self-care, and the ability to interact with others effectively and independently. It is appropriate for use up to 89 years of age.

#### **Exceptional assessment amendment – for Wave 1 only:**

We wish to collect some feedback on the impact of IMAGINE-1 for families as part of our study monitoring and evaluation. During this exceptional time, we also wish to understand the impact of COVID-19 on our cohort. We will exceptionally be administering additional short questionnaires at the first follow up timepoint (wave 1 only):

- **The CoRonavlrus Health Impact Survey (CRISIS, 10 min)**

We will use a subset of the parent/caregiver CRISIS questionnaire created by the NIH (Appendix B). This information will help us interpret the SDQ data collected during the global pandemic.

- **Study Impact Questionnaire (5 min)**

Short questionnaire collecting information on the behavioural, clinical, social and psychological impact of taking part in IMAGINE-1 (Appendix B).

#### **Workstream 2 (subset of cohort assessed during face to face visits):**

In Workstream 2 there will be one intensive follow-up face-to-face assessment, ~5 years after our initial research visit. The same detailed wide-ranging and multi-informant assessments we used in IMAGINE-1 will be employed, providing optimal opportunities for longitudinal analysis and understanding of the children's development. We will also re-assess the unaffected (control) siblings. As a thank you to families for taking part, a £30 online gift voucher will be sent to parents/consultee. The assessments have been shown to be acceptable to families as part of IMAGINE-1:

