Baseline	
Conducted as part of IMAGINE-1:
 
Workstream 1:
 
 
- Development and wellbeing questionnaire
 
- Strengths and Difficulties Questionnaire
 
- Adaptive behaviours assessment Schedule -3
 
- Everyday Feelings Questionnaire
 
- Comparison of IMAGINE mental health research data (from Workstream 1 questionnaires) with the Mental Health Children and Young People data of the general population (MHCYP, anonymous data from NHS Digital)
 
 
Workstream 2:
 
 
- Modified Lewis scale
 
- Child and Adolescent Psychiatric Assessment (CAPA)
 
- Autism Diagnostic Interview–Revised (ADI-R)
 
- Structured interview for Prodromal Symptoms (SIPS)
 
- Autism Diagnostic Observation Schedule (ADOS)
 
- Wechsler Abbreviated Scales of Intelligence-2nd Edition (WASI-II)
 
- Developmental Behaviour Checklist (DBC)
 
- Wisconsin Card Sorting Test (WCST)
 
- Cambridge Neuropsychological Test Automated Batter (CANTAB)
 
- Family Environment Scale
 
- Iowa Family Interaction Rating Scales
 
- Life Events Checklist
 
- Physical Health (including seizures and epilepsy) and medication use
 
- Development Coordination Disorder Questionnaire (DCDQ)
 
- Strengths and Difficulties Questionnaire (SDQ – parent and teacher reports)
 
- Social Communication Questionnaire (SCQ)
 
- Social Responsiveness Scale (SRS)
 
- Repetitive Behavior Scale Revised (RBSR)
 
- Pubertal development (Peterson assessment)
 
- Child Eating Behaviour Questionnaire (CEBQ) and the Hyperphagia Questionnaire (HQ)
 
- Epilepsy screening questionnaire (ESQ)
 
- Blood and saliva sample collection
 

Longitudinal follow up	
Workstream 1:
 
 
- Data linkage to Hospital Episode Statistics (HES)
 
- and Comparison of HES data of the IMAGINE and
 

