	
control cohorts (pseudonymised control data from individuals without intellectual disability, NHS Digital)
 
- Data linkage to National Pupil Database (NPD)
 
- Development and Wellbeing questionnaire
 
- Annual follow-up (for 5 years):
 
 
- Strengths and Difficulties Questionnaire
 
- Everyday Feelings Questionnaire
 
- Adaptive behaviours assessment Schedule
 
- Family Life Questionnaire
 
- Wessex Scales
 
- Demographic updates
 
- Impact of COVID-19 on mental health
 
- Study Impact Questionnaire
 
 
Workstream 2:
 
 
- Modified Lewis scale
 
- Child and Adolescent Psychiatric Assessment (CAPA)
 
- Autism Diagnostic Interview–Revised (ADI-R)
 
- Structured interview for Prodromal Symptoms (SIPS)
 
- Autism Diagnostic Observation Schedule (ADOS)
 
- Wechsler Abbreviated Scales of Intelligence-2nd Edition (WASI-II)
 
- Developmental Behaviour Checklist (DBC)
 
- Wisconsin Card Sorting Test (WCST)
 
- Computerised Neurocognitive Battery (CNB)
 
- Family Environment Scale
 
- Iowa Family Interaction Rating Scales
 
- Life events checklist
 
- Physical Health (including seizures and epilepsy) and medication use
 
- Development Coordination Disorder Questionnaire (DCDQ)
 
- Strengths and Difficulties Questionnaire (SDQ – parent and teacher reports)
 
- Social Communication Questionnaire (SCQ)
 
- Social Responsiveness Scale (SRS)
 
- Repetitive Behavior Scale Revised (RBSR)
 
- Pubertal development (Peterson assessment)
 
- Child Eating Behaviour Questionnaire (CEBQ)
 
- Hyperphagia Questionnaire (HQ)
 
- Epilepsy screening questionnaire (ESQ)
 
- Blood and saliva sample collection
 
- Eating Disorder Examination Adolescent Questionnaire (EDE-A)
 
- Pica, ARFID, and Rumination Disorder Interview (PARDI-AR-Q)
 
- ARFID brief screener (ARFID-BS)
 
- Nine Item ARFID screen (NIAS)
 

--	--

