### Wechsler Abbreviated Scale of Intelligence (WASI)

**This is an individually administered intelligence test suitable for individuals aged 6-89.** The WASI comprises four subtests (vocabulary, block design, similarities and matrix reasoning) and provides the following intelligence quotient (IQ) scores:

- **Verbal IQ score** - a measure of acquired knowledge, verbal reasoning, and attention to verbal information.
- **Performance IQ scores** – a measure of fluid reasoning, spatial processing, attentiveness to detail and visual-motor integration.
- **Full Scale IQ score** - the overall estimate of an individual's general level of intellectual functioning.

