i) We will model the trajectories for the psychopathological and neurocognitive measures using mixed models via an accelerated longitudinal design. We will test several models of longitudinal development including linear and non-linear effects. We have found evidence of considerable psychiatric comorbidity in children with pathogenic CNVs as well as between psychiatric and other neurodevelopmental traits (e.g., motor coordination). We therefore propose to use data reduction strategies as part of our analytical approach, combining highly correlated traits to create phenotypic clusters. We will reduce measures to critical developmental domains by applying principal components analysis to the individual-specific random effects for trajectory generated for each phenotypic measure in the mixed model analysis. This is similar to the approach successfully applied by our team's collaborators to derive measures of disease progression in Huntington Disease and has two main benefits: firstly, defining a more informative phenotypic measure, and secondly, reducing the multiple testing burden.

ii) The domain-specific trajectory measures will be compared between children with pathogenic CNV and their unaffected siblings using regression analysis.

iii) A similar regression analysis will be used to test for differences in trajectories between the 13 different CNVs.

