### **Neurocognitive Assessment**

#### **Wechsler Abbreviated Scale of Intelligence (WASI)**

The WASI is a general intelligence, or IQ test designed to assess specific and overall cognitive capabilities. It is a battery of three subtests: Vocabulary, Similarities and Matrix Reasoning. The Vocabulary and Similarities subtests are combined to yield a Verbal IQ score, and when combined with the Matrix Reasoning subtest this provides a Full Scale IQ Score.

The WASI provides the following intelligence quotient (IQ) scores:

- **Estimated Verbal IQ score:** A measure of acquired knowledge, verbal reasoning, and attention to verbal information.
- **Estimated Full Scale IQ score:** The overall estimate of an individual's general level of intellectual functioning).

IQ Score	<NAME>'s Score
Estimated Verbal IQ Score	
Estimated Full Scale IQ Score	

Each child's scores are compared with those of others of the same age. The average range for an IQ score at any age is between 90 and 109. This means that <NAME>'s IQ is <below average/average/above average.>

**Please note that this is an abbreviated measure of intelligence obtained for research purposes. It does not have the validity of a full-scale IQ assessment conducted by an educational psychologist.**

The assessment has been obtained for research purposes. Please do not use this report as a substitute for a clinical assessment.

youth//mind

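### Workstream 2 used CANTAB at baseline but gives the CNB at its only follow-up visit, so the computerised cognitive tests are not the same assessments and neither battery can show within-child change

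*Protocol*

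**What the plan says.** The claim of repetition is in section 5.5, Workstream 2: "The same detailed wide-ranging and multi-informant assessments we used in IMAGINE-1 will be employed, providing optimal opportunities for longitudinal analysis". The same paragraph fixes the number of occasions: "there will be one intensive follow-up face-to-face assessment, ~5 years after our initial research visit".

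The baseline battery in section 5.4 is the WASI, the WCST and "Cambridge Neuropsychological Test Automated Battery (CANTAB"; the synopsis baseline list also has CANTAB and no CNB. The synopsis follow-up list has "Computerised Neurocognitive Battery (CNB" and no CANTAB. Section 5.5 gives the WASI and the CNB as the follow-up neurocognitive assessment and sets out the CNB tests one by one.

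The analysis plan, section 6.1, Workstream 2, item i), says: "We will model the trajectories for the psychopathological and neurocognitive measures using mixed models via an accelerated longitudinal design". It then takes the individual trajectory random effects for each measure into a principal components analysis. Items ii) to v) use the resulting trajectory measures.

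Two further entries do not agree. The WCST is in the synopsis follow-up list but not in the section 5.5 neurocognitive assessment. The WASI is described in section 5.5 as "The WASI comprises four subtests (vocabulary, block design, similarities and matrix reasoning", with a Performance IQ, whereas the Participant Report template says "It is a battery of three subtests: Vocabulary, Similarities and Matrix Reasoning" and gives no Performance IQ. The synopsis names the WASI-II; sections 5.4 and 5.5 name the WASI.

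**The concern.** Change in cognition over time is part of Workstream 2's primary objective (synopsis and section 4.2). The analysis reaches it through a trajectory estimated for each child on each measure, and that needs at least two occasions on the same scale. A battery used only at visit 1 and another used only at visit 2 do not provide this.

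If the two were joined as one series, every baseline score would come from one test and every follow-up score from the other. Instrument would be completely confounded with time, and a child's apparent change would be the difference between two tests. If the CNB were entered alone, the so-called trajectory effect would be a restatement of the child's level. Either could pass into the principal components and then into the comparisons with siblings, between CNVs and with polygenic scores, and be reported as developmental change.

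**Working it through.** The plan gives no figure on this point to reproduce. The check is a comparison of the lists, then the consequence for the model.

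**Instruments by occasion**

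| | Baseline, synopsis | Baseline, 5.4 | Follow-up, synopsis | Follow-up, 5.5 |
|---|---|---|---|---|
| IQ | WASI-II | WASI | WASI-II | WASI |
| Card sorting | WCST | WCST | WCST | not listed |
| Computerised battery | CANTAB | CANTAB | CNB | CNB |

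On the last row synopsis and body agree at each occasion, so the change of battery is not a slip in one list.

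**Counts**

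- Baseline cognitive instruments repeated: 2 of 3 by the synopsis (WASI, WCST); 1 of 3 by section 5.5 (WASI).
- Follow-up scores listed in section 5.5: 11 CNB domains + 3 WASI IQ scores = 14. Without a same-instrument baseline: 11 of 14.

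**What one occasion gives**

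Write a child's deviation from the mean age curve as u0 + u1·a + e, where a is age minus 12 and the variances are s0², s1² and se². With one occasion the predicted slope is

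s1²·a / (s0² + s1²·a² + se²) × (the child's deviation).

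This is the child's level multiplied by a function of age. From such data s0² and se² cannot be separated, and s1² shows only as a change of variance with age. The accelerated design supplies a between-child age gradient, not an individual slope.

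**Illustration with assumed values** (none is in the protocol): s0 = 12, s1 = 1 per year, se = 6, all treated as known; u0 and u1 uncorrelated; baseline ages uniform on 6 to 13, the range the protocol gives for most children; follow-up 5 years later.

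- Two occasions on one instrument. The difference divided by 5 estimates the slope with error variance 2 × 36 / 25 = 2.88. From the difference alone, the squared correlation with the true slope is 1 / (1 + 2.88) = 0.26. Simulation using both scores fully gives 0.27.
- One occasion, at follow-up (a from −1 to 6). At a given a the squared correlation is a² / (144 + 36 + a²): 0 at a = 0 and 36 / 216 = 0.17 at a = 6. Averaged over the range it is 0.05, and simulation also gives 0.05.

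Even that 0.05 depends on variances and a zero correlation that single-occasion data cannot supply.

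**Power section.** With a noncentral F test and noncentrality N·R²/(1 − R²), the three 80% power statements come out at 85.5% (2% of variance, N = 650, alpha 0.01), 84.8% (5%, 12 degrees of freedom, N = 500, alpha 0.01) and 81.4% (3%, N = 500, alpha 0.0025). They are not in dispute, but they take a trajectory measure for each child as given.

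**The case against.** The strongest reply is that the damage is limited. IQ is repeated on every reading, and the synopsis lists the main psychopathology measures at both visits (CAPA, SIPS, ADI-R, ADOS, SDQ, DBC, SCQ). The primary objective covers cross-sectional variation as well as change, and the CNB serves the first. Item i) names no instrument. The planned contrasts are between groups, so a uniform shift from changing battery would be common to affected children and siblings. A method for linking the batteries would ordinarily sit in a statistical analysis plan, which is not shown.

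Much of this stands. The absence of a linkage method is not itself a finding. But section 5.5 makes a statement that its own lists contradict, and no analysis plan can create a second occasion on either battery. A common shift cancels only if the two batteries measure the same thing on equivalent scales in both groups, and nothing in the protocol supports that.

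A reader might go further in four ways that the documents do not support:

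- *That most planned neurocognitive trajectories are lost.* The protocol does not list them; it refers only to 5 trajectories in the power section. The share depends on counting: 11 of 14 scores, or 2 of 3 baseline instruments under section 5.5, but 1 of 3 under the synopsis.
- *That the WASI edition changes between visits.* The synopsis says WASI-II at both occasions and the body says WASI at both. The disagreement is between synopsis and body.
- *That IQ change is already known to mix different subtests.* The three-subtest text is in a feedback template for families, and the baseline subtests are stated nowhere.
- *That the WCST was omitted from section 5.5 by mistake.* It may have been dropped on purpose, since one CNB test also uses changing sorting principles with feedback. The protocol does not settle it.

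**Conclusion.** The point holds for the computerised battery. CANTAB is given only at baseline and the CNB only at the single follow-up, so the statement that the same assessments are repeated is wrong, and the individual trajectory effects planned in section 6.1 cannot be estimated as within-child change on either battery. In section 5.5 that covers 11 of the 14 listed follow-up cognitive scores.

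IQ change remains estimable, provided the WASI edition and subtests are settled. Card-sorting change is estimable only if the WCST is in fact given at follow-up.

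The conclusion rests on the instrument lists and the single follow-up visit, not on any power figure or on the illustrative variances.

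**What to change.** 1. Section 5.5: correct the sentence so that it excepts the computerised battery, naming CANTAB at baseline and the CNB at follow-up.
2. Section 6.1, Workstream 2, item i): state that neurocognitive trajectories, and the principal components analysis of their random effects, use only instruments given at both visits. Analyse the CNB as a cross-sectional follow-up outcome adjusted for baseline IQ. If CANTAB and CNB domains are to be joined instead, prespecify the linkage and acknowledge that instrument is fully confounded with time.
3. Reconcile the synopsis and section 5.5 on whether the WCST is given at follow-up. This should be settled while visits are still under way, because a missed repeat cannot be recovered.
4. Reconcile the WASI edition (synopsis against sections 5.4 and 5.5) and the subtests (section 5.5 against the Participant Report), and score IQ change from the subtests common to both visits.

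Items 1, 2 and 4 cost wording and analysis only. Item 3 is also wording unless the reconciliation changes what is administered. The scientific cost is that the longitudinal cognitive claim narrows to IQ, plus card sorting if the WCST is confirmed.
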